13.4.2 Primary Analysis of Primary Endpoint

We will use paired t-test or Wilcoxon signed-rank test to compare each immune parameter (innate immune responses) between D1 and D7 after first dose of vaccine, between D61 and D67 after second dose of vaccine, and D0 and D60 (at each dose of Zoster vaccine). The choice of the test will depend on the normality of the data, as judged by normal Q-Q plots.

13.4.3 Supportive Analyses of the Primary Endpoint(s)/Outcome(s)

N/A

13.4.4 Analyses of Secondary and Other Endpoint(s)/Outcome(s)

AE rates in each group will be summarized using frequency tables. Between-group comparison will be conducted using Fisher's exact test.

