3.5. Stratification, Randomization, and Blinding/Masking

60 subjects (n=30: 50-60 years old, n=30: ≥ 70 years old) will be enrolled in the study and will receive two doses of Zoster Vaccine Recombinant, Adjuvanted (Shingrix®) at D0 and D60. There will be no randomization, study participant or clinical study personnel blinding, or masking.

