13.2 Endpoints

Primary Endpoint

- Differences in innate immune signatures between D0, D1, and D7 and each dose of Zoster vaccine recombinant, adjuvanted, in both age cohorts.

Secondary Endpoint

- Differences in related adverse events and serious adverse events between each dose of Zoster vaccine recombinant, adjuvanted, in both age cohorts.

Exploratory Endpoints

- The changes in transcriptomics, metabolomics and immune cell populations between D0 (before vaccination) and D1, D3, D7, D14 and D30 after each dose of Zoster vaccine recombinant, adjuvanted, in both age groups
- The changes in the phenotype of T cell responses and the kinetics of these changes between D0 (before vaccination) and D7, D14 and D30 after each dose of Zoster vaccine recombinant, adjuvanted, as well as D180 and D270+ (optional visit) in both age groups.
- The changes in the magnitude of activated B cells, antibody secreting cells and memory B cells and the kinetics of these changes between D0 (before vaccination) and D7, D14 and D30 after each dose of Zoster vaccine recombinant, adjuvanted, as well as D180 and D270+ (optional visit) in both age groups.
- The changes in VZV serology between D0 (before vaccination) and D14 and D30 after each dose of Zoster vaccine recombinant, adjuvanted, as well as D180 and D270+ (optional visit) in both age groups.
- The changes in specificity, magnitude and phenotype of VZV-specific (gE and other antigens) T cells and the kinetics of these changes between D0 (before vaccination) and 7, 14, 30 days after each dose of Zoster vaccine recombinant, adjuvanted, and at D180 and D270+ (optional visit) in both age groups.
- The changes in magnitude of VZV-specific B cells and the kinetics of these changes between D0 (before vaccination) and 7, 14, 30 days after each dose of Zoster vaccine recombinant, adjuvanted, and at D180 and D270+ (optional visit) in both age groups.
- Baseline stool microbiome alpha and beta diversity parameters.

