13.4 Analysis Plan

Data from the study will be analyzed using the statistical software R. High-throughput data will be analyzed using appropriate methods, either by stand-alone software or modules in leading statistical software, e.g. the Bioconductor in the R framework. For cytokine data, missing values will be dealt with using multiple imputations. For gene expression and metabolomics data, nearest neighbor method and local least squares may be used to fill missing values. Unsupervised learning techniques such as PCA, PLSDA, clustering, and factor analysis will be used for the visualization and identification of global patterns. For descriptive endpoints, we will generate summary statistics, and visualize the data using histograms and boxplots when applicable. For the identification of innate signatures, the two age groups will be analyzed separately.

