13.4.1 Analysis Populations

We will use all subjects who receive at least the first dose of the vaccine, and have measurements at days 0 and day 30 after the vaccination in the data analysis.

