13.4.6 Descriptive Analyses

The log₂ antibody titers of each group at each time point will be summarized and presented using histograms and strip charts for visual comparison. AE rates in each group will be summarized by tabulation.

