13.7 Sample Size Considerations

For sample size consideration, we will use the alpha level of 0.01 for the immune parameters. Given less than 50 immune parameters will be tested, this alpha level translates to an expected count of false positives of <1, which is an acceptable level. For the gene expression data and for sample size consideration only, we will use the alpha level of 0.0005 to offset the effect of multiple testing. This means an average of one false positive for every 2000 null genes tested; given ~20,000 genes will be measured, this alpha level translates to an expected 10 false positives. We expect >100 genes will be truly differentially expressed. Thus among all genes called differentially expressed, the proportion of false positives will be <10%, which is an acceptable level in gene expression studies. We note this consideration is for sample size analysis alone. In actual data analysis false discovery rate (FDR) will be used.

For the traditional immune parameters, with 30 samples in a treatment group, we can reject the null hypothesis of equal means with 80% power if the true effect size (mean difference/sigma) is 0.66, using a two-sided paired t-test and the alpha level of 0.01. For the gene expression, the actual data analysis will be performed using the false discovery rate. For simplicity, for sample size consideration, we will consider the simpler case of a paired t-test. With 30 samples in a treatment group, we can reject the null hypothesis of equal means with 80% power if the true effect size (mean difference/sigma) is 0.88, using a two-sided paired t-test and the alpha level of 0.0005.

For unpaired test, with sample size of 30 per group, at the alpha level of 0.01, we can reject the null hypothesis of equal means with 80% power if the true effect size ((mean0-mean1)/sigma, assuming equal variance) is 0.91 using an unpaired two-sided t-test.

For a paired t-test, with the sample size of 30, at the alpha level of 0.01, we can reject the null hypothesis of no change with 80% power if the true effect size (mean difference/sigma) is 0.66.

For correlation analysis, with 30 samples in the treatment group, at the alpha level of 0.01, we can reject the null hypothesis of zero correlation with 80% power if the true correlation is 0.57 using a two-sided test for Pearson's correlation coefficient.

14. Identification and Access to Source Data

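### Wrong as written: the only secondary endpoint compares adverse events between doses, but the plan analyses them only by 'group', with an unpaired test

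*Combined protocol and SAP*

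**What the plan says.** Section 13.2, the synopsis and section 3.3 give one secondary endpoint: "Differences in related adverse events and serious adverse events between each dose of Zoster vaccine recombinant, adjuvanted, in both age cohorts". Section 3.5 says that the 60 subjects "will receive two doses of Zoster Vaccine Recombinant, Adjuvanted", at D0 and D60, without randomization.

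The analysis of that endpoint is in section 13.4.4: "AE rates in each group will be summarized using frequency tables. Between-group comparison will be conducted using" Fisher's exact test. Section 13.4.6 adds "AE rates in each group will be summarized by tabulation". Neither section mentions dose, and neither defines *group*.

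Section 13.4.1 gives the only analysis population: "We will use all subjects who receive at least the first dose of the vaccine, and have measurements at days 0 and day 30" after vaccination. No separate safety population is named.

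On collection, section 12.2.1 sets 7 days for solicited AEs and 30 days for unsolicited AEs after each dose, with SAEs collected to the end of the study. Section 8.1 puts participation at 6 months, with an optional later visit.

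**The concern.** The endpoint asks whether the same people have more related AEs or SAEs after one dose than after the other. The analysis text never splits AEs by dose and never mentions pairing. The immune analyses in 13.4.5 are written for each dose with paired tests, so the omission is specific to AEs.

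Followed literally, the plan would leave its only secondary endpoint without an analysis of its own, or would give it a test for independent samples. The between-dose analysis would then have to be chosen after the AE data had been seen. The question is a real one: section 5.1 reports more headache and shivering after dose 2 than after dose 1.

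The population rule raises a second problem. A person who is vaccinated and has AEs but no day 30 measurement falls outside the only population defined, and so outside the AE rates.

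**Working it through.** The plan states no power, alpha or sample size for AEs, so there is no figure of its own to reproduce.

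**1. What *group* means.** Section 13.4 says "For the identification of innate signatures, the two age groups will be analyzed separately". Section 13.4.6 separates group from time: "antibody titers of each group at each time point will be summarized". Section 13.7 says "with 30 samples in a treatment group, we can reject the null hypothesis of equal means with 80% power", and 30 is the size of an age cohort. With no randomization and one vaccine, age cohort is the natural reading.

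- *Group* = age cohort: Fisher's test is valid for 30 versus 30 independent people, but it compares cohorts, not doses.
- *Group* = dose: the two samples are the same people. With positive within-person correlation, Fisher's test rejects too rarely. Assume a true 20% rate after both doses, n=60 and two-sided alpha 0.05. At correlation 0 / 0.3 / 0.5, its simulated rejection rate is 3.0 / 0.9 / 0.2%; exact McNemar gives 3.0 / 2.6 / 2.2%.

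A small example shows why the pairing matters. With n=30, 6 people with an event after dose 1 and 12 after dose 2, Fisher gives p=0.158 however the people overlap. Exact McNemar ranges from p=0.031 (discordant pairs 0 v 6) to p=0.238 (6 v 12).

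**2. What a paired analysis could deliver.** Inputs: shivering p1 = 0.138 and p2 = 0.214 (section 5.1, ages pooled); within-person correlation r assumed 0.3 to 0.5. One partial check on r comes from section 5.1, which gives 26.8% shivering overall. If that means after either dose, with similar denominators, the proportion with both is 0.138 + 0.214 − 0.268 = 0.084, and r = (0.084 − 0.138×0.214)/0.1415 = 0.39.

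Formulas:
- p11 = p1·p2 + r·√[p1(1−p1)p2(1−p2)], where the root is √(0.138×0.862×0.214×0.786) = 0.1415
- p10 = p1 − p11; p01 = p2 − p11; d = p2 − p1 = 0.076
- half-width = 1.96·√[(p10 + p01 − d²)/n]

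| r | p11 | p10 | p01 | p10+p01−d² | n=30 | n=60 |
|---|---|---|---|---|---|---|
| 0.3 | 0.0720 | 0.0660 | 0.1420 | 0.2023 | 0.161 | 0.114 |
| 0.5 | 0.1003 | 0.0377 | 0.1137 | 0.1457 | 0.137 | 0.097 |

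The half-width is thus 14 to 16 points per cohort and 10 to 11 pooled, against a difference of 7.6 points. Section 5.1 says solicited symptoms were less frequent at 70 and older. At half the pooled rates (assumed), the n=30 half-width is 10 to 12 points. Exact McNemar power for the 7.6-point difference, at two-sided alpha 0.05 and r of 0.3 / 0.5, is 5.8 / 4.9% at n=30 and 16.8 / 21.2% at n=60.

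**3. Follow-up by dose.** The 7-day and 30-day windows in 12.2.1 are equal for the two doses. SAE follow-up is not. With dose 2 on D60 and the last visit on D180, it is 60 days after dose 1 and 180 − 60 = 120 days after dose 2. Section 8.5 allows a late second dose at a missed vaccination visit, while 8.6 times D180 from the first dose. A second dose on D90 gives 90 v 90 days; on D120 it gives 120 days after dose 1 and 60 after dose 2.

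**4. Appendix D against the text.** Its adverse-event row appears blank at D60 and marked at D180. D180 lies beyond 30 days after either on-schedule dose. Section 12.2.1 also collects procedure-related AEs for 24 hours after each blood draw. That could explain the D180 mark, but blood is drawn at D60 too. The table may have been damaged in extraction, so this needs checking against the original.

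**The case against.** The strongest defence is proportion. The secondary objective is only to assess safety, in an open-label mechanistic study of a licensed vaccine. AEs are recorded after each dose, so tables by dose can be produced at any time, and no realistic analysis at n=30 would be decisive. This bears on the weight of the point. It does not remove the mismatch, because the plan still names a test and that test is either aimed at another question or unpaired.

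The day 0 and day 30 condition may well be meant for assay data. That is plausible, but no other population is defined, and sections 6.5 and 8.5 show that some people may receive only one dose. Those sections do not show that day 30 data will be lost.

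The documents do not support some stronger readings:

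- *The plan builds in a two-fold SAE excess after dose 2.* The 120 v 60 days hold only for on-schedule dosing and can reverse with a late second dose. No section plans a raw SAE count by dose, and *related* in the endpoint may also qualify SAEs, which would limit a background-rate argument.
- *Fisher's test would create false safety signals.* Under the dose reading it errs the other way.
- *Safety oversight is weakened.* Collection, ISM review and holds (11.5, 12.4, 12.8.2) do not depend on this analysis.

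**Conclusion.** Wrong as written. The analysis in 13.4.4 and 13.4.6 does not match the secondary endpoint in 13.2: on the plan's usual meaning of *group* it answers a different question, and on the other meaning it ignores the pairing and is conservative. This rests on the text alone.

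The loss is a pre-specified estimate, not a powered test. The precision figures assume the pooled shivering rates in 5.1, correlation 0.3 to 0.5, and all subjects receiving both doses; the n=60 figures also assume the same rates in both cohorts. A reader might infer that a paired test would rescue the comparison. It would not, since the pooled half-width still exceeds 7.6 points.

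The population rule is a defect of wording. Whether it would bias AE rates, and by how much, cannot be determined from the documents.

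**What to change.** 1. In 13.4.4, state that *group* is age cohort and keep Fisher's test for that comparison only.
2. In 13.4.1, limit the D0/D30 condition to the immune analyses. Analyse AEs in everyone given at least one dose, with dose 1 rates among dose 1 recipients and dose 2 rates among dose 2 recipients.
3. Tabulate related AEs and SAEs by dose within cohort, saying whether SAEs are limited to related ones. Among two-dose recipients, report the dose 2 minus dose 1 difference with a 95% CI for paired proportions, per cohort and pooled. Exact McNemar is optional support.
4. Use the same post-dose window for both doses in the between-dose comparison, including SAEs, and list later SAEs separately. Reconcile the adverse-event row of Appendix D with the 30-day windows in 12.2.1 and 12.4.1.

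The cost is SAP wording and minor analysis work, with no new data. Intervals stay wide. One-dose recipients fall outside the paired estimate, so their dose 1 AEs should be listed beside it. SAEs after the common window fall outside the between-dose comparison.

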13.4.5 Analyses of Exploratory Endpoint(s)/Outcome(s)

Exploratory Endpoint 1. The innate immune response signatures are identified from traditional immune parameters, gene expression measured by RNA-seq experiment, and metabolomics data measured by LC/MS. The innate signatures will be identified for the two age groups separately. The traditional immune parameters, genes, and metabolites that change significantly over baseline after immunization are considered innate signatures.

Traditional markers will be tested using paired t-test or Wilcoxon test against D0, and significant markers will be considered part of the innate immune signature.

RNA-seq data will be preprocessed using Bowtie and Tophat, and FPKM (fragments per kilobase of exon model per million mapped reads) values will be calculated. Gene level comparison of D1, D4, D14 and D30 vs D0 will be conducted using DESeq to find the transcriptomics signature of vaccination.

Metabolomics data will be processed using packages apLCMS, XCMS, and xMSAnalyzer and generate data tables containing accurate mass m/z , retention time(s), intensity, coefficient of variation, and

related descriptive characteristics, including minimal information standards for metabolomics data. SAM(8) and similar methods will be used to detect differential abundance of features between D1, D4, D14 and D30 vs D0 to select metabolic innate signatures.

After each vaccination, the innate signatures that are correlated with the D30 antibody titers are considered correlation signatures of the innate immune responses. The correlation will be assessed using Spearman's correlation and the associated p-values.

Exploratory Endpoint 2. We will use paired t-test or Wilcoxon test to compare each immune parameter (changes in phenotype of T cell responses and the kinetics of these changes) between D7, D14 and D30 after vaccination and D0 for each dose of Zoster vaccine.

Exploratory Endpoint 3. We will use paired t-test or Wilcoxon test to compare each immune parameter (changes in the magnitude of activated B cells, antibody secreting cells and memory B cells and the kinetics of these changes) between D7, D14 and D30 after vaccination and D0 for each dose of Zoster vaccine.

Exploratory Endpoint 4. We will use paired t-test or Wilcoxon test to compare VZV serology between D14, D30, D180 and D270+ (optional visit) after vaccination and D0 for each dose of Zoster vaccine.

Exploratory Endpoint 5. We will use paired t-test or Wilcoxon test to compare each immune parameter (changes in specificity, magnitude, and phenotype of VZV-specific T cells and the kinetics of these changes) between D7, D14, D30, D180 and D270+ (optional visit) after vaccination and D0 for each dose of Zoster vaccine.

Exploratory Endpoint 6. We will use paired t-test or Wilcoxon test to compare each immune parameter (changes in magnitude of VZV-specific B cells and the kinetics of these changes) between D7, D14, D30, D180 and D270+ (optional visit) after vaccination and D0 for each dose of Zoster vaccine.

Although our statistical methods will adhere to what is proposed herein, our experience with analyses of similar studies in the past has underscored the need for flexibility and adaptability in trying different statistical approaches to arrive at the most informative results. As such, we may use alternative approaches such as the gene set enrichment analyses, or other approaches, in an *ad hoc* basis.

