3.4. Exploratory Endpoint(s)/Outcome(s)

- The changes in transcriptomics, metabolomics and immune cell populations between D0 (before vaccination) and D1, D3, D7, D14 and D30 after each dose of Zoster vaccine recombinant, adjuvanted, in both age groups.
- The changes in the phenotype of T cell responses and the kinetics of these changes between D0 (before vaccination) and D7, D14 and D30 after each dose of Zoster vaccine recombinant, adjuvanted, as well as D180 and D270+ (optional visit), in both age groups.
- The changes in the magnitude of activated B cells, antibody secreting cells and memory B cells and the kinetics of these changes between D0 (before vaccination) and D7, D14 and D30 after each dose of Zoster vaccine recombinant, adjuvanted, as well as D180 and D270+ (optional visit), in both age groups.
- The changes in VZV serology between D0 (before vaccination) and D14 and D30 after each dose of Zoster vaccine recombinant, adjuvanted, as well as D180 and D270+ (optional visit), in both age groups.
- The changes in specificity, magnitude and phenotype of VZV-specific (gE and other antigens) T cells and the kinetics of these changes between D0 (before vaccination) and 7, 14, 30 days after each dose of Zoster vaccine recombinant, adjuvanted, and at D180 and D270+ (optional visit), in both age groups.
- The changes in magnitude of VZV-specific B cells and the kinetics of these changes between D0 (before vaccination) and 7, 14, 30 days after each dose of Zoster vaccine recombinant, adjuvanted, and at D180 and D270+ (optional visit), in both age groups.
- Microbiome parameters in stool collected at baseline. These will be correlated to the immune responses to the Zoster vaccine to assess whether the stool microbiome may be related, and possibly influence immune responses.

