4.4. Selection of Clinical Sites/Labs

The study will be conducted at The Hope Clinic, the clinical arm of the Emory Vaccine Center at Emory University.

Address:

[name]
[name]

Samples may be processed at the following laboratories:

[name], Stanford University, California
[name], La Jolla Institute, California
[name], Emory University, Atlanta, GA

5. Known and Potential Risks and Benefits to Participants

5.1. Risks of Investigational Product or Intervention as cited in Investigator Brochure or Package Insert

In clinical trials involving a pooled cohort of 29,305 subjects above 50 years of age who received at least one dose of Shingrix[®] (n=14,645) or saline (n=14,660) administered to a 0- and 2-month schedule, the following adverse reactions have been seen:

- Local adverse events: pain (78%), redness (38.1%), swelling (25.9%)

- General adverse event: myalgia (44.7%), fatigue (44.5%), headache (37.7%), shivering (26.8%), fever (20.5%), and gastrointestinal symptoms (17.3%).

The incidence of solicited local and general symptoms was lower in subjects aged 70 years and older compared with those aged 50 to 69 years.

The majority of solicited local adverse reactions and general adverse events seen with Shingrix® had a median duration of 2 to 3 days.

Headache and shivering were reported more frequently by subjects after Dose 2 (28.2% and 21.4% respectively) compared with Dose 1 (24.4% and 13.8% respectively). Grade 3 solicited general adverse events (headache, shivering, myalgia and fatigue) were reported more frequently by subjects after Dose 2 (2.3%, 3.1%, 3.6% and 3.5% respectively) compared with Dose 1 (1.4%, 1.4%, 2.3% and 2.4% respectively).

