5.3. Risks of Other Protocol Specified Medications

We do not anticipate the use of any other medication; however, should anaphylactic or hypersensitivity reactions occur, epinephrine (1:1000) and diphenhydramine injections are readily available at the Hope Clinic during vaccine use.

Epinephrine injection can be associated with high blood pressure, arrhythmia, lightheadedness, nervousness, restlessness, tremor, shortness of breath and diaphoresis. The frequency of these side effects is not defined. Diphenhydramine injection may be required to treat possible allergic reactions and its use can be associated with low blood pressure, arrhythmia, confusion, dizziness, sedation, restlessness, diarrhea, nausea and urinary retention. The frequency of these side effects is also not defined.

When facing a medical emergency, the clinic staff will follow the institutional SOP by calling 911 first. If needed, the subject will be transferred to Emory University Emergency Department for further care.

Subjects are allowed to receive acetaminophen or nonsteroidal anti-inflammatory drugs (NSAIDs) if they experience a moderate to severe local or systemic side effects after vaccine administration. The use of these medications will be recorded as concomitant medications.

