7.1.2. Other permitted concomitant medications

Subjects are allowed to use acetaminophen or nonsteroidal anti-inflammatory drugs (NSAIDs) if they experience a moderate to severe local or systemic side effects after vaccine administration.

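### The innate-signature rule has no step to separate drug-derived features from vaccine effects, so acetaminophen or NSAID metabolites in early post-dose samples can be called vaccine signatures

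*Combined protocol and SAP*

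**What the plan says.** Exploratory Endpoint 1 in Section 13.4.5 sets one criterion: "The traditional immune parameters, genes, and metabolites that change significantly over baseline after immunization are considered innate signatures". For conventional markers it adds: "Traditional markers will be tested using paired t-test or Wilcoxon test against D0, and significant markers will be considered part of the innate immune signature". For metabolites, SAM and similar methods "will be used to detect differential abundance of features between D1, D4, D14 and D30 vs D0 to select metabolic innate signatures". Signatures are identified separately in the two age groups of 30 (Sections 13.4 and 13.4.5). Those that correlate with D30 antibody titer become the correlation signatures.

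Section 7.1.2 states: "Subjects are allowed to use acetaminophen or nonsteroidal anti-inflammatory drugs (NSAIDs) if they experience a moderate to severe local or systemic side effects". Section 5.3 gives the same permission and adds: "The use of these medications will be recorded as concomitant medications". The Schedule of Events has medication reviewed at every visit, and participants are told to call when they start or stop a drug.

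No part of Section 13.4 refers to the medication record. Section 13.4.3 (supportive analyses of the primary endpoint) reads N/A. Everyone is vaccinated, so there is no comparator group.

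**The concern.** A drug taken between D0 and a post-dose draw brings its own parent compound and breakdown products into an untargeted LC/MS table. If they are absent or low at D0 and raised in users afterwards, they meet the signature rule as written. Section 5.1 gives a median reaction duration of 2 to 3 days, so intake can fall before the first post-dose draws. Such a feature would enter the metabolic signature list and become a candidate for correlation with D30 titer.

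Use may also be unequal across cohorts and doses. Section 5.1 reports that "The incidence of solicited local and general symptoms was lower in subjects aged 70 years and older compared with those aged 50 to 69 years", and that Grade 3 general events were more frequent after Dose 2. A drug feature could pass in one age group or after one dose and not in the other, and a reader comparing the lists could take this for a difference in innate response.

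**Working it through.** **The plan's own figures (Section 13.7).** Noncentral-t power of a two-sided paired t-test with n = 30 is 79.7% for effect size 0.66 at alpha 0.01, and 79.8% for 0.88 at 0.0005. Both stated values of 80% reproduce and are not in dispute. The same two levels serve below as approximate thresholds.

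**Users needed for a flag.** Let k of n = 30 carry a feature raised by an equal amount, with zero change in the rest. The paired statistic is t = sqrt(k(n − 1)/(n − k)).

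- Alpha 0.01, critical t 2.756: k = 6 gives sqrt(6 × 29/24) = 2.69; k = 7 gives sqrt(7 × 29/23) = 2.97. So 7 users (23%).
- Alpha 0.0005, critical t 3.918: k = 10 gives sqrt(10 × 29/20) = 3.81; k = 11 gives sqrt(11 × 29/19) = 4.10. So 11 users (37%).
- Signed-rank with zeros dropped, p = 2 × (1/2)^k: k = 8 gives 0.0078 and k = 12 gives 0.00049. So 8 and 12 users.

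**Chance of that many users.** The documents give no rate of analgesic use, so it is varied as an assumption: the share taking one given drug before one given draw. The probabilities are binomial tails with n = 30.

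| Assumed use | At least 7 users (0.01) | At least 11 users (0.0005) |
|---|---|---|
| 10% | 3% | <0.1% |
| 20% | 39% | 3% |
| 30% | 84% | 27% |
| 40% | 98% | 71% |

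**With noise.** For a rise of 5 SD of change in users, simulation of the paired t-test flags the feature at 0.01 in 68% of runs with 8 users and 96% with 10. At 0.0005 the figures are 3% and 20%.

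**Use split over drugs.** Each drug has its own features, so the count must be reached drug by drug. If 30% use divides evenly over two drugs, 15% take each. The chance of at least 7 users is then 15.3% per drug, so at most 2 × 15.3% = 30.6% that either reaches it. The chance of at least 11 is 0.3% per drug.

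**Endogenous markers.** If the drug moves a host marker by 1 SD in users only, the marker is flagged in 5%, 12% and 23% of runs at 20%, 30% and 40% use (alpha 0.01), and in about 2% at 30% use (alpha 0.0005).

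**Cost of excluding users.** At 30% use, n falls to 21. Power falls to 58% for 0.66 at 0.01 and to 48% for 0.88 at 0.0005.

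**The case against.** The strongest reply is that the size is unknown and easily overstated. Much of it stands.

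- A reader might infer from Section 5.1 that moderate to severe reactions are common. It gives no such rate. It gives any-grade rates (pain 78%, myalgia 44.7%) and Grade 3 general rates of 1.4% to 3.6% per symptom per dose. The any-grade figures also pool the doses: headache is 37.7% overall but 24.4% after Dose 1 and 28.2% after Dose 2. They do not size use before one draw.
- Metabolites are to be tested with SAM, and Section 13.7 reserves 0.01 and 0.0005 for sample size, with false discovery rates in the actual analysis. The table is therefore approximate. Analgesic use at D0 is not excluded by Section 4.3 and would weaken the contrast with baseline.
- A reader might infer that the primary endpoint is compromised. Section 13.4.2 does not test D1 against D0. It plans to "compare each immune parameter (innate immune responses) between D1 and D7 after first dose of vaccine", D61 against D67, and D0 against D60. A drug effect on host markers could reach the D1 and D61 samples, but the flag rates above are low.
- A reader might infer a false age difference in a planned test. Signatures are called within each age group, and no between-age test of innate signatures is planned. Only an informal comparison of lists is exposed.
- D3 is a doubtful exposure point. The endpoint covers "The changes in transcriptomics, metabolomics and immune cell populations between D0 (before vaccination) and D1, D3, D7, D14 and D30", but the written gene and metabolite contrasts name D4, for which no visit exists. These must be reconciled; meanwhile D1 is the clear case.

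What does not stand is reliance on false discovery rate control or on the ad hoc flexibility at the end of Section 13.4.5. The first limits chance findings, and a drug metabolite's rise is not one. The second commits the analysts to nothing.

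**Conclusion.** The gap holds. The rule has no attribution step, the drugs are permitted before the draws, and the recorded use plays no part in the analysis. Drug-derived LC/MS features can be reported as innate signatures. The documents do not support saying that they will be. At about 10% use of one drug a flag is unlikely. At 30% to 40% it is likely at 0.01 (84% to 98%) and ranges from 27% to 71% at 0.0005, in the noise-free case with all use in one drug. Splitting across drugs, noise and the actual SAM procedure would change these figures. The metabolite route is the firm part; effects on endogenous markers and the primary contrasts are possible but weakly supported. The point deserves correction because the remedy is cheap and the misreading would not show in the planned output.

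**What to change.** Add to Section 13.4.5:

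1. Before signatures are called, annotate the LC/MS features and remove those identified as acetaminophen or NSAID parents or metabolites. Flag, but keep, other features seen only in samples with recorded use. Use follows reactogenicity, so deleting these could discard genuine reaction-linked biology.
2. Keep all participants in the main analysis, so that planned power is unchanged. Add a supportive repeat that excludes post-dose samples taken after recorded analgesic use since that dose, or that includes use as a covariate. Compare effect estimates and intervals, not significance alone: a signature may drop out of the smaller set merely because power has fallen from 80% to about 58% (30% use, effect size 0.66, alpha 0.01), or because the more reactogenic participants have been left out.
3. At the early post-dose visits (D1, D3, D7, D61, D63, D67), record the date and time of last analgesic intake on the existing concomitant-medication form.

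The cost is some SAP wording, one annotation step, one repeat analysis and one form field. The first two items can use existing records; the intake time must be collected prospectively. What participants may take is unchanged.
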